### 12.1. Serious Adverse Event

A serious adverse event (SAE) refers to any untoward medical occurrence that at any dose (including those after the signing of ICF and prior to dosing):

- Results in death
- Is life-threatening (patient is at immediate risk of death at the time the event occurs)
- Requires hospitalization (official hospitalization for medical reason) or prolongation of existing hospitalization
- Results in permanent or significant disability/incapability
- Results in a congenital anomaly/birth defect

Important medical events that may not result in death, are not life-threatening, or do not require hospitalization may be considered SAEs when, based upon appropriate medical judgment, they may jeopardize the patient and may require medical or surgical intervention to prevent one of the outcomes listed in this definition. Examples of such medical events include allergic bronchospasm requiring intensive treatment in an emergency room or at home, blood dyscrasias or convulsions that do not result in inpatient hospitalization, or the development of drug dependency or drug abuse.

TEAE-unrelated hospitalizations due to elective procedures or other medical procedures during treatment will not be regarded as SAEs.

Sudden death and death unexplained should be reported as an SAE.

Progression of malignancy (including lethal outcomes) during the study period or within the safety reporting period should not be reported as an SAE.

Hospitalizations due to the following events will not be regarded as SAEs:

- Routine treatment or monitoring of the indications studied, is not related to any conditions aggravated.
- Blood or platelet transfusion for routine treatment of the indications studied; however, hospitalization or prolongation of existing hospitalization due to complications of transfusion should still be reported as an SAE.
- Procedures related to study protocol/disease-related examinations (e.g., surgery, scan, endoscopy, sampling for laboratory tests, bone marrow sampling). However, hospitalization or prolongation of existing hospitalization due to complications of these procedures should still be reported as an SAE.
- Hospitalization or prolongation of existing hospitalization for technical, practical or social reasons in the absence of an AE.

- Pre-defined procedures (i.e., scheduled prior to initiation of study treatment); must be recorded in the source documents. However, hospitalization or prolongation of existing hospitalization due to complications should still be reported as an SAE.
- Elective treatment for an existing sickness that is unrelated to the indications studied.

### **12.1.1. Follow-up of AE and SAE**

All AEs occurring during the study period should be followed up according to the Good Clinical Practice, until the events are resolved, stabilized, or judged as no longer clinically significant, or until the patient is medically stable or the event is a chronic disease. Any AE assessed as study drug-related must be followed up until it is resolved or stabilized.

### **12.1.2. Post-study AE and SAE**

The Investigator should follow up all unresolved events until the event is resolved, the patient is lost to follow-up, or there is another explanation for the AE. At the last scheduled visit, the Investigator should instruct each patient to report any subsequent events that the patient or the patient's personal physician believes to be reasonably related to participation in this study.

Before the end of the study, the Investigator should notify the Antengene Pharmacovigilance Department (see Section 12.1.3.1) of any death or AE that occur at any time after a patient has discontinued or terminated participation in the study and that may be reasonably related to this study.

After the end of the study, the Investigator should notify Antengene or its designee of any death or AE that occur at any time after a patient has discontinued or terminated participation in the study and that may be reasonably related to this study. If the Investigator becomes aware of the development of cancer or a congenital anomaly in the subsequently conceived offspring of a patient who has participated in this study, Antengene should also be notified.

### **12.1.3. Report of Serious Adverse Events**

#### **12.1.3.1. Reporting Requirements**

For any SAE in any patient, the Principal Investigator or designated study site personnel must report to the Antengene Pharmacovigilance Department (within 24 hours following initial awareness of the event or awareness of the follow-up information), relevant regulatory authorities, and relevant ethics committee. The study sites will be asked to provide the following information:

- Study Protocol No
- Study site and/or Investigator number
- Demographic data
- Brief description of the event
- Date and time of onset (if applicable)
- Date and time of resolution (if applicable), if the event is resolved
- Current status, if the event is not resolved yet
- Any concomitant therapy and medication
- Investigator's assessment on the correlation between the SAE and investigational product
- Event outcome, if available

All other Investigators participating in the ongoing study drug clinical study will submit the copies of these reports to their Institutional Review Board (IRB) Ethics Committee (EC) after receiving them, if applicable. According to the standard operating procedures and the policies of IRB/EC, the Investigator will report all the SAEs to IRB/EC. Adequate records must be kept to demonstrate that IRB/EC has been properly notified.

## **12.2. Overdosage**

Overdose refers to the intentional or unintentional administration of study drug to a study patient using a dose level higher than that is allocated to that individual patient per the study protocol. In the event of drug overdose, the Investigator and Antengene should be notified immediately, and the patient's AEs should be closely monitored. The patient should receive symptomatic treatment as appropriate, and the overdose event and related AEs and/or treatment should be recorded in the patient's medical record. In addition to recording the overdose in the patient's medical record, the event must be reported to the Antengene Pharmacovigilance Department using the Overdose/Medication Error Report Form. Any AE or SAE due to overdose observed will be handled as described in Section 12.2 (if applicable).

Because ATG-010 is metabolized via GSH binding, it is predicted that hepatic GSH depletion may occur in the case of overdose. Therefore, in patients with abnormal liver function test, use of supportive measures such as SAM 400 mg by oral administration, 1-4 times/day, or other drugs that can replace GSH, should be considered.

Medication errors, and administrations of study drug outside the predictable range of the study protocol, including drug misuse and abuse, must also be reported to the Antengene Pharmacovigilance Department using an Overdose/Medication Error Report Form.

## **12.3. Pregnancy**

Pregnancy itself will not be regarded as an AE, unless it is reasonably believed that the investigational drug may interfere with the effectiveness of contraceptive medication.

Each pregnancy in any patient treated with ATG-010 or patient's partner should be reported to Antengene within 24 hours following the awareness of the event. The pregnancy should be followed up to find out the outcome, including natural or voluntary termination of pregnancy, delivery details, and presence or absence of any birth defects, congenital anomalies, or maternal and/or newborn complications. Pregnancy must be followed up and recorded, even if the patient withdraws from or completes the study.

It is advised that male patients should avoid to father a child within 3 months from termination of ATG-010 treatment. There is currently no information about the effects of ATG-010 on reproductive capacity, pregnancy, or subsequent fetal development.

Any pregnancy found within the period from the start of study medication to 3 months post study medication should be reported to the Investigator and the Sponsor.

## 13. Statistical considerations

### 13.1. Overall Considerations

#### 13.1.1. Statistics and Analysis Plan

This section describes the statistical analyses to be used for evaluating the efficacy and safety endpoints of this trial. For the analysis details, please refer to the Statistical Analysis Plan (SAP).

Listings of appropriate disposition, demographic, baseline, efficacy and safety parameters will be generated. For categorical variables, the number and percentage of patients in each parameter category (including the missing data category), as well as two-sided 95% confidence interval (CI) as appropriate, will be presented in the form of summary table. For continuous variables, the number of patients, mean, median, standard deviation (SD), minimum, and maximum values will be provided. Time to event data will be summarized by Kaplan-Meier (KM) method, using 25th, 50th (median), and 75th percentiles with two-sided 95% CIs, and percentage of censored observations.

Primary analysis (including efficacy, safety, and PK evaluations) will be conducted at 3 months after the last patient enrollment, and supplementary efficacy and safety analysis will be conducted after the end of the study.

An interim analysis will be performed when approximately 50 patients have completed the clinical efficacy evaluations to assess the distribution of the patients who had previously received RRMM treatment. During the interim analysis, the clinical efficacy in patients who had previously received 3 classes of drugs (at least an immunomodulatory [i.e., lenalidomide], at least a protease inhibitor [i.e., bortezomib], and at least an anti-CD38 antibody) should be analyzed, but the efficacy for whole population enrolled will not be analyzed.

#### 13.1.2. Sample Size Determination

This trial is a bridging clinical study to evaluate the clinical efficacy of ATG-010 plus low-dose dexamethasone in Chinese patients with relapsed/refractory MM.

A sample size of 82 subjects with relapsed/refractory MM who have previously been treated with immunomodulatory agent and proteasome inhibitors (i.e., including lenalidomide and bortezomib) will allow for detecting a statistical significance of the target ORR of 28% against the threshold ORR of 15%, with power of 80% (one-sided  $\alpha=0.025$ ).

#### 13.1.3. Patient Disposition

A summary of patient disposition will be provided, including the number of patients in each analysis population, the number of patients with unevaluable disease per IMWG criteria, the number of patients censored at each of PFS and OS analyses, the number of lost to follow-up patients, the number of patients who discontinued before completing the study, and the reasons for discontinuation.

#### 13.1.4. Blinding and Randomization

This is an open-label, single-arm study, therefore blinding and randomization are not applicable.

### **13.1.5. Dose Adjustment**

Dose modifications that occurred during the first treatment cycle and throughout the entire clinical study process will be analyzed. Meanwhile, an exploratory analysis of the effects of dose modification on efficacy may be performed.

## **13.2. Analytical Dataset**

### **13.2.1. Analysis Population**

#### **13.2.1.1. Modified Intent-to-treat (mITT) Population**

The modified intent-to-treat (mITT) population will include patients who received at least one dose of study treatment. This population will be used for efficacy analysis.

#### **13.2.1.2. Per Protocol Population**

The Per Protocol (PP) population will include all patients in the mITT population who meet the following criteria:

- Have an ATG-010 compliance  $\geq 70\%$ ,
- Have at least 1 complete post-baseline response assessment, unless died or withdrew from study before that.
- Have no major protocol deviation that would compromise the efficacy evaluation. The list of major protocol deviations affecting statistical analysis will be finalized before database lock.

Major protocol deviations and their impact on efficacy evaluation will be determined independent of knowledge of treatment response before database lock and study analyses. This population will be used for supportive efficacy analysis; however, if there are significant differences between the results of this population and those obtained in the mITT population, the efficacy evaluation will take these differences into account.

#### **13.2.1.3. Safety Population**

The safety population will include patients who have received at least one dose of study treatment.

#### **13.2.1.4. Subgroup Efficacy Analyses**

Subgroup comparisons of special interest will be assessed according to the Statistical Analysis Plan (SAP).

## **13.3. Data Analysis and Presentation**

The disposition of patients participating in this clinical study, and the demographic and baseline characteristics, efficacy and safety data described in the section below will be presented in the form of summary tables. All relevant data collected via the eCRF and labs will be provided in the patient data listings.

### **13.3.1. Demographic Characteristics**

The demographic characteristics of mITT, PP, and safety populations will be summarized, including gender, race, ethnicity, and age at the time of informed consent. For gender and race, summary

statistics will include the number and percentage of patients within each category. The race category is a classification recorded in the database. For age at the time of informed consent, the mean, median, minimum, maximum, and standard deviation of each patient population will be provided.

### **13.3.2. Baseline Characteristics and Medical History**

Baseline characteristics include performance status, duration from initial diagnosis, response to prior therapy, types of prior therapy, and body height/body weight. Baseline data will be tabulated using the summary statistics for the mITT, PP, and safety populations; formal hypothesis testing will not be performed.

Baseline medical history and physical examination results for the same analysis populations will be presented in summary tables.

### **13.3.3. Primary Endpoint**

The primary efficacy endpoint of ORR (proportion of patients who achieve PR, VGPR, CR, or sCR) based on mITT population and response assessment by IRC will be analyzed. For the hypothesis testing of the target ORR of 28% against the threshold ORR of 15%, a two-sided 95% confidential interval of the ORR will be provided. A lower bound of this interval >15% will indicate statistical significance of the test. ORR will also be analyzed based on the response assessments made by Investigator.

### **13.3.4. Secondary Endpoints**

The following secondary efficacy endpoints for the mITT and PP populations will be analyzed separately.

- Survival rate (SR) at 6, 9, and 12 months
- Duration of response (DOR) = Duration from the first observation of at least partial response (PR) to time of disease progression (PD) or death due to PD, whichever comes first. DOR for death due to any reasons other than PD will be censored.
- Clinical benefit rate (CBR) = CBR+minimal response [MR], and duration of clinical benefit (duration from the first observation of at least MR to PD or death due to PD, whichever comes first). Duration of clinical benefit for death due to any reasons other than PD will be censored.
- Disease control rate (DCR) = CBR+stable disease [SD; for at least 12 weeks])
- Progression-free survival (PFS) = Duration from start of study treatment to PD or death [irrespective of cause of death], whichever comes first)
- Time to progression (TTP) = Duration from start of study treatment to time of PD
- Overall survival (OS) = Duration from start of study treatment to death

The Kaplan-Meier (KM) method will be used to analyze the time to event endpoints (including duration of response, PFS, TTP, and OS), including the median estimate, 25th and 75th percentiles, and two-sided 95% CIs. The CBR and DCR will be summarized using two-sided 95% confidence intervals.

In addition, the following secondary endpoints of safety and tolerability will be analyzed using the Safety Analysis Set.

- Safety and tolerability will be analyzed per National Cancer Institute (NCI)-Common Terminology Criteria for Adverse Events (CTCAE) v 4.03.
- The ATG-010 PK profile of this patient population will be described.
- Cytogenetic and fluorescence in situ hybridization (FISH) prognostic markers, including chromosomal aberrations [e.g., del17p, t(4;14), t(14;16), del13] and other cytogenetic categories of MM.

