### Secondary endpoints

#### a. Efficacy:

- Survival rate (SR) at 6 months, 9 months, and 12 months
- Time to progression (TTP): Duration from start of study treatment to time of disease progression
- Progression-free survival (PFS): Duration from start of study treatment to PD or death (regardless of cause), whichever comes first
- Duration of response (DOR): Duration from the first observation of at least PR to time of disease progression, or deaths due to disease progression, whichever occurs first
- CBR: Proportion of patients who achieve sCR, CR, VGPR, PR, or minimal response (MR)
- DCR: Proportion of patients who achieve sCR, CR, VGPR, PR, MR, or stable disease (SD; for a minimum of 12 weeks)
- OS (Kaplan-Meier estimates)
- MRD in patients who achieve CR and sCR
- The effect of risk factors stratification based on fluorescence in situ hybridization (FISH) on clinical efficacy, including del 13, del 17p13, t(4;14), t(14;16), 1q21 amplification

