13 Telephone call (or visit) with patient to evaluate supportive care medications, concomitant medications and adverse events, and to adjust supportive care as appropriate. The telephone contact with the patient must take place on C1D3 (following administration of first dose of ATG-010 on C1D1). Survival follow up should be conducted via telephone call or in-person contact with the subject every 3 months until death or study discontinuation. MM disease status, survival, subsequent antineoplastic therapy, and drug-related SAE data will be collected at these phone calls/visits.

14 The end of treatment (EoT) visit is considered to be  $\leq$ 14 days after the last medication, and if it is more than 14 days after the last medication, the EoT visit will be performed within 1 week when the Investigator judges that the subject has permanently terminated the study drug.

15 After treatment discontinuation, if possible, for patients who are not progressing, SPEP with serum immunofixation, UPEP (24 h) with urine protein immunofixation, serum FLC, and quantitative Ig levels should be performed every 3 months for 1 year to assess durability of response.

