#### 6.2.2. Secondary Endpoints

a. Efficacy:

- SR at 6 months, 9 months, and 12 months
- TTP: Duration from start of study treatment to time of disease progression
- PFS: Duration from start of study treatment to PD or death (regardless of cause), whichever comes first
- DOR: Duration from the first observation of at least PR to time of disease progression, or deaths due to disease progression, whichever occurs first.
- CBR: Proportion of patients who achieve sCR, CR, VGPR, PR, or minimal response (MR)
- DCR: Proportion of patients who achieve sCR, CR, VGPR, PR, MR, or stable disease (SD; for a minimum of 12 weeks)
- OS (Kaplan-Meier estimates)
- MRD in patients who achieve CR and sCR
- The effect of risk factor stratification based on fluorescence in situ hybridization (FISH) on clinical efficacy, including del 13, del 17p13, t (4;14), t (14;16), 1q21 amplification

b. Safety and tolerability

c. PK: including but not limited to ATG-010 Cmax and tmax

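### Duration of response and of clinical benefit censor deaths not due to progression; add an all-cause version and a count of those deaths

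*Combined protocol and SAP*

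**What the plan says.** In Section 13.3.4, DOR runs from the first response of PR or better to progression (PD) or death due to PD, and "DOR for death due to any reasons other than PD will be censored". For the second duration, which starts at MR or better, the section says: "Duration of clinical benefit for death due to any reasons other than PD will be censored". Section 6.2.2 gives the same DOR event set: "DOR: Duration from the first observation of at least PR to time of disease progression, or deaths due to disease progression, whichever occurs first". The synopsis does too: "Duration of response (DOR): Duration from the first observation of at least PR to time of disease progression, or deaths due to disease progression".

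Kaplan-Meier medians and quartiles are planned for the time-to-event endpoints, and the secondary efficacy endpoints are analysed in the mITT and PP populations (13.3.4). The outputs that bear on the censored deaths are these:

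- Section 13.1.1 asks for the "75th percentiles with two-sided 95% CIs, and percentage of censored observations". It does not ask for reasons for censoring.
- Section 13.1.3 counts patients censored for PFS and OS. It does not name DOR.
- Sections 13.3 and 13.3.6.1 provide patient listings, including a listing of deaths.
- Section 13.3.4 also plans TTP (PD only) and PFS (PD or any death), both timed from start of treatment.

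On cause of death, Section 12.1 separates fatal progression from other deaths for safety reporting: "Progression of malignancy (including lethal outcomes) during the study period or within the safety reporting period should not be reported as an SAE", while "Sudden death and death unexplained should be reported as an SAE". Analysis detail is deferred to a separate SAP (13.1.1, 13.2.1.4, 13.3.7), and the review committee's procedures to a charter (7.2). Neither text is in the supplied document.

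**The concern.** Median DOR is usually read as how long a response lasts. A responder who dies without PD has no response left to lose, so that death is a competing event and not ordinary loss of follow-up. Censoring it lets the Kaplan-Meier curve carry on as if the patient could still progress later.

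What is at stake is interpretation. From a median and one overall censoring percentage, a reader cannot separate responders who died without PD from responders still in response at the cut-off. The rule also makes the event status of a death before documented PD depend on its attributed cause, and no supplied section describes independent adjudication of that cause. Deaths after documented PD raise no such question, because DOR has already ended.

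**Working it through.** **Plan's own figure.** The plan states no figure for DOR. Its sample size does reproduce: with 82 patients and success at 20 or more responders, exact binomial power at 28% is 0.801 and the one-sided error at 15% is 0.0172. The number of responders used below is 82 × 0.28 = 22.96, about 23.

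**Direction.** At an event time with n at risk, d_PD progressions or PD deaths and d_D other deaths, the planned curve is multiplied by (1 − d_PD/n) and the all-cause curve by (1 − (d_PD + d_D)/n). The risk sets are the same and the first factor is never smaller. The planned curve therefore lies on or above the all-cause curve, and its median is equal or longer. This needs no assumption about the hazards. Equality holds if there are no such deaths or if they do not move the median.

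**Size.** Let f be the share of response-ending events that are non-PD deaths. The documents give no f, so the range is assumed. Under constant hazards the planned median is ln 2/λ_PD and the all-cause median is ln 2/(λ_PD + λ_D), so their ratio is 1/(1 − f).

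| f | Ratio | Planned median longer by |
|---|---|---|
| 0 | 1.00 | 0% |
| 0.05 | 1.05 | 5% |
| 0.10 | 1.11 | 11% |
| 0.20 | 1.25 | 25% |
| 0.30 | 1.43 | 43% |

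**Expected counts for DOR.** Inputs from the documents:

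- enrolment of about 6 months (synopsis, Study Duration);
- primary analysis 3 months after the last enrolment (13.1.1);
- study end when all patients reach 12 months (7.5).

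Assumptions:

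- uniform enrolment and no drop-out;
- response 1 month after start, guided by the 4-week median time to response in Section 4.2.2;
- an all-cause median of 6 months, with 4 to 8 as the range, which has no source in the documents;
- follow-up of responders continuing to study end.

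Follow-up after response is then uniform on (a, b). At the primary analysis it is 3 to 9 months from start less 1, so (2, 8). At study end it is 12 to 18 less 1, so (11, 17).

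Expected events = 23 × [1 − (e^(−ha) − e^(−hb)) / (h(b − a))], with h = ln 2/median. At a median of 6 months, h = 0.1155 and h(b − a) = 0.6931.

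- Primary analysis: 23 × [1 − (0.7937 − 0.3969)/0.6931] = 9.83.
- Study end: 23 × [1 − (0.2806 − 0.1403)/0.6931] = 18.34.

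The last column below is exp(±1.96/√events), the approximate 95% interval for the all-cause median relative to its estimate.

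| Analysis | Events (medians of 4 and 8 months) | Non-PD deaths at f = 0.05, 0.10, 0.20, 0.30 | Interval factors |
|---|---|---|---|
| Primary | 9.8 (12.9, 7.9) | 0.5, 1.0, 2.0, 2.9 | 0.54 to 1.87 |
| Study end | 18.3 (20.9, 16.1) | 0.9, 1.8, 3.7, 5.5 | 0.63 to 1.58 |

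Even the ratio of 1.43 at f = 0.30 lies inside both intervals.

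**Simulation check.** With 23 responders, a 6-month all-cause median, the two follow-up windows and the four non-zero values of f (4,000 trials each, 32,000 in all), the planned median was never below the all-cause median. It was strictly longer in about 13%, 24%, 40% and 52% of trials at the primary analysis, and in about 44%, 70%, 91% and 98% at study end, in order of f.

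Counts for duration of clinical benefit are not worked out, because the plan gives no expected rate of MR. The direction and the 1/(1 − f) ratio apply there in the same way.

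**The case against.** The strongest reply is that this is a choice of estimand. The rule is explicit and pre-specified, the three DOR definitions agree, and nothing in the protocol says that DOR measures time alive and in response. That stands: a reader might infer an error, or a contradiction with PFS, but the documents support neither. PFS counts all deaths by its own definition. It does not replace an all-cause DOR, because it starts at first dose and is not restricted to responders.

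A reader might also blame the longer median on the missing sensitivity analysis. That is wrong. The inequality comes from the censoring rule and would remain after the fix; the missing outputs only hide its size.

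Nor is it right that nothing planned bears on these deaths. If TTP and PFS otherwise share censoring rules, PFS events minus TTP events count the deaths without prior PD across the trial, which is an upper bound for those among responders. The listings would allow an all-cause DOR to be rebuilt. What is missing is a planned summary at responder level.

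Finally, the separate SAP may already contain the analysis, and the review committee's charter may cover cause of death. Both remain open, so the absence claimed here is limited to the supplied text.

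**Conclusion.** The point holds as a low-cost improvement, a change that could be made. By construction, the planned medians for both durations equal or exceed the median time alive and in response (or in clinical benefit). The excess is about 5% to 43% if non-PD deaths are 5% to 30% of response-ending events and hazards are constant, and zero if there are none. The range for f and the 6-month median are assumptions.

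It would be tempting to conclude that DOR will be materially overstated or that the trial's conclusion is at risk. The documents do not support that. The shift is within sampling error for about 23 responders, DOR is descriptive, and the ORR decision rule in 13.3.3 does not use it. The reason to act is that the confidence interval shows sampling error but not a shift that can go in only one direction. Confidence is medium, mainly because the SAP text was not available.

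**What to change.** Keep the present definition and endpoint names. Add to the SAP, or confirm that it already contains:

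*Sensitivity analysis: DOR and duration of clinical benefit will also be estimated by Kaplan-Meier with death from any cause as an event, and the number of patients censored because of non-PD death will be reported for each duration.*

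If the SAP already has this, a cross-reference in 13.3.4 is enough. If the sponsor prefers to label the endpoint cause-specific, the label should go into the synopsis, 6.2.2 and 13.3.4 alike, so that the names do not diverge. TTP can stay as it is.

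Cost: about four tables (two durations in the mITT and PP populations) and a possibly shorter median alongside the planned one. No new data are needed, since footnote 13 of Table 1 already states that "MM disease status, survival, subsequent antineoplastic therapy, and drug-related SAE data will be collected at these phone calls/visits". The SAP is the lighter route: a protocol amendment needs written ethics approval before implementation (14.5), and a departure from a SAP that is already final must be recorded in the study report (13.4). Specifying the analysis before results are known also keeps the choice from looking data-driven.

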### Appendix 3. International Myeloma Working Group Response Criteria, Myeloma

**Table 10: International Myeloma Working Group Response Criteria (Kumar 2016)**

Standard IMWG Response Criteria 	
Response subcategory	Response criteria
Complete Response (CR)	Negative IFE of serum and urine, disappearance of any soft tissue plasmacytomas (SPD), and <5% plasma cells in bone marrow aspirates
Stringent Complete Response (sCR)	CR as defined above plus normal FLC ratio  and absence of clonal cells in bone marrow biopsy by immunohistochemistry ( $\kappa/\lambda$ ratio $\leq 4:1$ or $\geq 1:2$ for $\kappa$ and $\lambda$ patients, respectively, after counting $\geq 100$ plasma cells  )
Very Good Partial Response (VGPR)	Serum and urine M-protein detectable by IFE but not on electrophoresis, or $\geq 90\%$ reduction in serum M-protein plus urine M-protein level $<100$ mg per 24 hours
Partial Response (PR)	$\geq 50\%$ reduction of serum M-protein plus reduction in 24-hour urine M-protein by $\geq 90\%$ or to $<200$ mg per 24 hours. If the serum and urine M-protein are unmeasurable, a $\geq 50\%$ decrease in the difference between involved and uninvolved FLC levels is required in place of the M-protein criteria. If serum and urine M-protein are unmeasurable, and serum FLCs are also unmeasurable, $\geq 50\%$ reduction in plasma cells is required in place of M-protein, provided baseline bone marrow plasma cell percentage was $\geq 30\%$ . In addition to the above criteria, if present at baseline, a $\geq 50\%$ reduction in the size (SPD) of soft tissue plasmacytomas is also required 
Minimal Response (MR)	$\geq 25\%$ but $<49\%$ reduction of serum M-protein, and reduction in 24-h urine M-protein by 50-89%. In addition to the above criteria, if present at baseline, a $\geq 50\%$ reduction in the size (SPD) of soft tissue plasmacytomas is also required 
Stable Disease (SD)	Not recommended for use as an indicator of response; stability of disease is best described by providing the TTP estimates. Not meeting criteria for CR, VGPR, PR or progressive disease

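### Section 13.3.4 defines CBR in terms of itself, and Table 10 leaves a one-point serum gap between MR and PR: minor wording errors that touch secondary endpoints only

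*Combined protocol and SAP*

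**What the plan says.** **CBR and DCR.** Section 13.3.4 has "Clinical benefit rate (CBR) = CBR+minimal response [MR" and, in the next bullet, "Disease control rate (DCR) = CBR+stable disease [SD; for at least 12 weeks". The same section adds a "duration of clinical benefit (duration from the first observation of at least MR to PD or death due to PD, whichever comes first". CBR and DCR are to be reported with two-sided 95% confidence intervals.

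The synopsis defines the first rate differently: "CBR: Proportion of patients who achieve sCR, CR, VGPR, PR, or minimal response (MR". Section 6.2.2 repeats that definition, and for the second rate gives "DCR: Proportion of patients who achieve sCR, CR, VGPR, PR, MR, or stable disease (SD; for a minimum of 12 weeks".

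**Response categories.** Sections 9.2 and 9.3 make the IMWG table in Appendix 3 (Table 10) the basis for assessing response, and Section 9.3 lists MR and SD as separate categories. In Table 10:

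- MR needs a serum M-protein reduction of at least 25% but below 49%, together with a 24-hour urine reduction of 50-89%.
- PR needs a serum reduction of at least 50%, together with a urine reduction of at least 90% or to below 200 mg per 24 hours.
- SD is residual: "Not meeting criteria for CR, VGPR, PR or progressive disease".

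**Primary endpoint.** Section 13.3.3 bases ORR on PR or better, as assessed by the IRC.

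**The concern.** Section 13.3.4 is where the CBR analysis is specified, and its formula cannot be used as it stands. It also disagrees with the two places that define CBR properly, and the DCR line is built on the same term.

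The Table 10 problem is separate. The MR and PR serum bounds should meet, and they do not. A patient just short of PR drops past MR into SD, below patients with smaller reductions. That patient leaves the CBR numerator, counts in DCR only if SD lasts at least 12 weeks, and has no start date for duration of clinical benefit until some other assessment reaches MR. Rounding to whole percentages does not help, because a bound of below 49% excludes 49% itself.

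**Working it through.** **1. The plan's own power figure.** Inputs (Sections 13.1.2 and 13.3.3): N = 82, threshold 15%, target 28%, one-sided alpha 0.025, success if the lower 95% limit exceeds 15%. Find the smallest r with P(X ≥ r | 82, 0.15) ≤ 0.025.

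- r = 19: tail probability 0.0328, Clopper-Pearson lower limit 14.56%. Fails.
- r = 20: tail probability 0.0172, lower limit 15.58%. Passes.
- Power = P(X ≥ 20 | 82, 0.28) = 0.8012.

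The stated 80% reproduces. ORR counts PR or better, and the PR serum bound of 50% is not in question, so nothing below alters these figures.

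**2. The CBR formula.** Taken literally, CBR = CBR + MR holds only if MR = 0. With ORR as the first term it matches the way Section 4.2.1 computes the rate:

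- All myeloma patients: 1 sCR + 6 PR + 13 MR = 20; 20/81 = 24.7% (stated as up to 25%).
- Combination patients: 1 sCR + 5 PR + 2 MR = 8; 8/25 = 32.0% (as stated).

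Putting CBR = ORR + MR into the DCR line gives sCR, CR, VGPR, PR, MR or SD of at least 12 weeks, which is the Section 6.2.2 definition.

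**3. Table 10 as written** (no progression, no plasmacytoma, urine residual at or above 200 mg per 24 hours in the first three rows):

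| Serum reduction | Urine reduction | MR row | PR row | Category |
|---|---|---|---|---|
| 48.9% | 60% | met | not met | MR |
| 49% | 60% | not met | not met | SD |
| 49.5% | 60% | not met | not met | SD |
| 50% | 90% | not met | met | PR |

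**4. Effect of one patient.** Table 3 gives CBR counts of 19 (FLC) and 29 (non-FLC): 48/122 = 39.3%, and 0.393 × 82 = 32.3, so take 32 as an example.

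- 32/82 = 39.0% (exact 95% CI 28.4 to 50.4).
- 31/82 = 37.8% (exact 95% CI 27.3 to 49.2).
- Difference 1/82 = 1.2 points.

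**5. How many patients might be in the band.** Assume that MR patients' serum reductions are spread evenly over the 24 points from 25% to 49%, and that the same density continues for one more point. Then expected number = MR share × 82 / 24.

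| Source of MR share | Share | MR patients in 82 | Expected in band |
|---|---|---|---|
| Section 4.2.1, combination, 2/25 | 8.0% | 6.56 | 0.27 |
| Table 3, non-FLC only, (29 − 17)/122 | 9.8% | 8.07 | 0.34 |
| Table 3, all, (48 − 32)/122 | 13.1% | 10.75 | 0.45 |
| Section 4.2.1, all, 13/81 | 16.0% | 13.16 | 0.55 |

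The non-FLC row fits best, because the bound applies to serum M-protein. On average, CBR shifts by 0.27/82 = 0.3 to 0.55/82 = 0.7 points. The Poisson chance of at least one such patient is 1 − exp(−0.27) = 0.24 to 1 − exp(−0.55) = 0.42, so zero is the most likely number.

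**The case against.** **The CBR line is an evident slip.** The synopsis and Section 6.2.2 give the full definition, Section 4.2.1 uses it, and the text is marked as a translation. This stands: the intended meaning is recoverable, and the result does not change for anyone who follows Section 6.2.2. Section 13.1.1 also refers details to a SAP, and no separate SAP text on this point could be checked. The line in the analysis section is still unusable as printed.

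**The IRC works to the IMWG criteria, and the footnotes to Table 10 refer questions of interpretation to that guideline.** This also stands in part. Whether the 49% is a transcription error can be settled only from the cited source. What the protocol alone shows is that its printed table leaves a one-point serum gap.

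**The expected count leans high.** It treats everyone seen in the band as lost. CBR counts patients who achieve a response, and disease is assessed on Day 1 of every cycle, so an earlier or later assessment may still qualify. This stands.

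A reader might also infer three stronger things that the documents do not support:

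- *That leaving MR out of the SD row distorts CBR or DCR.* It does not. A patient who meets MR has achieved MR whatever the SD row says, and DCR includes both categories with each patient counted once. Only the best-response table could be blurred. The absence of sCR from that row does not matter either, because sCR is CR plus further conditions.
- *That the urine bounds are equally wrong.* They are stated as 50-89% and at least 90%, and they meet at whole percentages. The serum bounds do not.
- *That closing the serum gap would give every serum reduction a category.* It would not, because MR and PR also carry urine conditions. A serum reduction of 55% with a urine reduction of 60% and at least 200 mg per 24 hours remaining would still meet neither.

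**Conclusion.** Two wording errors hold, and both are minor.

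- The CBR formula in Section 13.3.4 is circular and contradicts the synopsis and Section 6.2.2. It has no numeric effect if analysts use Section 6.2.2.
- The MR and PR serum bounds in Table 10 leave 49% to under 50% in neither category, so such a value is classed as SD and excluded from CBR and from the start of duration of clinical benefit. The size is 1.2 points of CBR for each patient with no other qualifying assessment. The illustration of about 0.3 to 0.55 such patients rests on an assumed even spread of reductions and on MR shares from the earlier studies, and it should be read as leaning high.

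One might suspect that a fault in the response table reaches the primary result. It does not: ORR, its test, N = 82 and the 80% power are unaffected. MR is also named in inclusion criterion 3, but without reference to Table 10, so nothing is claimed there.

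**What to change.** - **Section 13.3.4:** write CBR = ORR + MR (sCR, CR, VGPR, PR or MR). The DCR line then agrees with Section 6.2.2 and needs no rewriting.
- **Appendix 3, Table 10:** check the MR row against the cited IMWG criteria, and make its upper serum bound meet the PR lower bound (at least 25% to below 50%).
- **Optional:** add MR to the categories that the SD row excludes. This clarifies the best-response table and changes neither CBR nor DCR.

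The cost is a few words in two places, with no change to conduct, sample size or the primary analysis. The edits should be made before database lock, so that in an open-label study they cannot look driven by the data.
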